[¹¹C]Acetate Positron Emission Tomography (PET) in patients with Lymphangioleiomyomatosis (LAM) and Tuberous Sclerosis Complex (TSC).

NCT05467397

5/29/2024

Principal Investigator: [name]., Ph.D.

Associate Investigators: [name]
[name]

Research Contact: [name]., Ph.D.

Duration of study: 6 months

Number and type of subjects: 8 or 16 adult female subjects diagnosed with an angiomyolipoma

Ionizing radiation: Yes

Project uses IND/IDE: IND no. 146871

Multi-Institutional Project: No

Participating Institutions: Brigham and Women's Hospital, Boston, MA;
Massachusetts General Hospital, Boston, MA

I. Background and Significance

- a. **Historical Background:** Lymphangioleiomyomatosis (LAM) is a rare, multisystem disease of women, consisting of a diffuse proliferation of smooth muscle actin-positive cells (LAM cells), which harbor inactivating mutations in either the *TSC1* or *TSC2* tumor suppressor gene. These inactivating mutations result in constitutive activation of mammalian/mechanistic TOR (target of rapamycin) complex 1 (mTORC1) (2-5), which integrates growth factor and nutrient signaling to stimulate cell growth and metabolism (6-10). Pulmonary LAM is characterized by associated progressive cystic destruction of the lung parenchyma, recurrent pneumothorax, and chylous pleural effusions. Extrapulmonary proliferative lesions of LAM include renal angiomyolipomas and lymphangioleiomyomas. LAM can occur as a sporadic disorder where LAM cells harbor somatic inactivating mutations of the *TSC1* or *TSC2* gene, or in women with Tuberous Sclerosis Complex (TSC). TSC is an autosomal dominant disease characterized by neurologic manifestations and hamartomas of the brain, skin, heart, and kidneys (11). Up to 80% of women with TSC have radiologic evidence of cystic lung degeneration (11, 12).
- b. **Previous pre-clinical or clinical studies leading up to and supporting the proposed research:** Preclinical work was conducted in the laboratory of [name] and published in part in Clinical Cancer Research (1). The [name] lab was able to show that lipogenic pathways can be detected in preclinical models of TSC and LAM *in vivo* using microPET-based metabolic imaging
- c. **Rationale behind the proposed research and potential benefits to patients and/or society:** Rapamycin is an FKBP12-dependent allosteric inhibitor of mTORC1 approved by the FDA for the treatment of LAM and TSC-associated renal angiomyolipomas. Clinical trials of TSC and LAM have shown that 12 month-treatment with rapamycin induces response of renal angiomyolipomas and stabilization of pulmonary function and clinical benefit is seen after 3 months for both LAM and renal angiomyolipomas (13-15). However, lung function decline and tumor growth resume when treatment is interrupted. In addition, magnitude of clinical response to rapamycin varies across patients. For instance, in the EXIST-2 trial (double-blind, placebo-controlled, phase 3 trial) the response rate was 42%, with the primary efficacy endpoint being the proportion of patients with confirmed angiomyolipoma response of at least a 50% reduction in total volume of target angiomyolipomas relative to baseline (14).
This clinical evidence highlights the critical need for sensitive and specific biomarkers of response to therapy and/or disease progression, including biomarkers of tumor metabolic activity. Currently, elevated levels of vascular endothelial growth factor-D (VEGF-D) in the blood of LAM patients represent the only biomarker with diagnostic role in LAM (16, 17) and potentially a role as a biomarker of therapeutic response to mTORC1 inhibitors (18). However, not all LAM patients have clinically significant blood VEGF-D levels.
Metabolic imaging biomarkers of disease activity are not currently available for TSC/LAM. [¹⁸F]fluorodeoxyglucose (FDG)- PET has shown utility to identify malignant neoplasms including malignant perivascular epithelioid cell tumors (PEComas), primary lung cancers, and lymphomas, in patients with TSC and/or LAM. However, TSC and LAM lesions (renal angiomyolipomas, pulmonary LAM, lymphangioleiomyomas) did not show abnormal FDG

uptake, likely due to aberrant trafficking of glucose transporters (19-21). LAM patients would benefit from a metabolic imaging biomarker in multiple ways. *First*, a sensitive and specific imaging biomarker would help answer outstanding questions regarding personalized dosage and length of treatment for rapamycin and its analogs (rapalogs). *Second*, biomarkers of disease progression and therapeutic response would streamline the design, cost and duration of LAM/TSC clinical trials. *Third*, a metabolic imaging biomarker and circulating VEGF-D could be used as complementary diagnostics to enhance clinical decision making.

Fourth, PET is a technique already widely used in the clinics, therefore there will be no need to generate Intellectual Property or secure additional funding to commercialize any product of our study.

II. Specific aims

The proposed study aims to quantitatively and non-invasively assess metabolic activity of renal angiomyolipomas as an early biomarker of response to rapamycin and rapalogs and to implement modeling of LAM lung metabolic activity in LAM and TSC patients using [¹¹C]acetate positron emission tomography (PET) imaging.

These milestones will be achieved in the following Specific Aim:

Specific Aim 1. Test feasibility of [¹¹C]acetate PET to quantify metabolic activity of LAM or TSC patient lesions before and after treatment with rapamycin or rapalogs. We plan to enroll eight women with LAM or TSC who have renal angiomyolipomas and are rapamycin-naïve. Our preliminary studies reveal that incorporation of acetate in TSC2-deficient cells is strongly suppressed by rapamycin. In addition, our proof of concept preclinical studies with the acetate derivative fluoroacetate showed rapid uptake of this tracer by TSC2-deficient tumors, including tumors generated with LAM patient renal angiomyolipoma-derived cells, using dynamic PET.

In the proposed study, dynamic [¹¹C]acetate PET/CT will be used to monitor metabolic activity over time and to extract blood and tissue density components in renal (angiomyolipomas) and lung lesions in LAM or TSC patients. Patients enrolled who are either on treatment with Rapamycin or a rapalog or not will receive 1 scan each and patients who are about to start therapy with rapamycin or rapalogs, will receive 2 scans, one at baseline and one after 3 months of therapy

We expect to achieve the following outcomes:

1. Implement quantitative modeling to detect [¹¹C]acetate uptake in renal angiomyolipoma and pulmonary LAM.
2. Test [¹¹C]acetate PET as a biomarker of rapamycin activity in TSC2-deficient proliferative lesions.

Both outcomes will provide standardized uptake value (SUV) as a measure of metabolic activity of different LAM/TSC lesions in patients.

Our success will be measured as the ability to non-invasively detect and quantify metabolic activity of proliferative lesions in LAM or TSC patients. Importantly, enhanced uptake of [¹¹C]acetate has been reported in 10 patients with renal angiomyolipomas, showing

significantly higher SUV in the tumors compared to normal kidney. SUV was not affected by fat content (1). This published report supports the clinical feasibility of our proposed study.

III. Subject Selection

a. Inclusion/Exclusion Criteria: LAM or TSC patients, aged 18 yrs and over presenting with at least one renal angiomyolipoma (at least 1 cm in each diameter) confirmed by CT, MRI, or ultrasound and have not received any prior treatment with Rapamycin or rapalogs or candidates for initiating treatment with rapalogs or who have been on rapamycin or rapalogs for a minimum of 3 months and maximum of 5 years will be eligible for the study. Patients with LAM and AML who are currently on rapalogs for < 3 months and > 5 year and patients who have participated in other research studies in the past 12 months that have involved radiation exposure, which is more than 50 mSv/year, would not be eligible for this study.

b. Source of subjects and recruitment methods:

Patients are referred to our clinic at the LAM center at Brigham and Women's hospital by local pulmonologists as well as the LAM foundation for their clinical care. All clinic patients found to have an angiomyolipoma and other potential participants referred to us by physicians who care for LAM or TSC patients at various institutions and by the LAM foundation or the Tuberous Sclerosis Alliance could be approached for participation in the study. Care will be taken to allow potential subjects to feel free from tension and subtle coercion. The physician investigators will advise potential subjects that a study is being done, and briefly describe the study to ascertain interest prior to identifying themselves as being involved. Investigators will emphasize that participation is voluntary and that not participating will not jeopardize their future care at Brigham and Women's hospital or any other Partners institution.

The study investigators will also contact providers outside of these institutions who may be caring for patients with LAM or TSC to notify them of the clinical trial design, inclusion and exclusion criteria. This contact will be in the form of a letter to referring physicians. Such physicians will be provided with contact information of key personnel in the trial in order to refer potential subjects for participation.

IV. Subject Enrollment

The primary specialist or health care provider, usually a physician, who is known to the potential subject and has firsthand knowledge of the patient's medical history must (1) give approval for his/her patient to be contacted for research purposes (2) initially introduce the study to the patient and (3) obtain the patient's permission to be contacted by study staff. A nurse or study coordinator will review the informed consent with the subject to avoid the possibility of coercion or bias since subjects will be recruited from Investigator's own practice. Subjects will be reminded that refusal to participate in this trial will not change the quality of care that she will receive at BWH. Study participation is voluntary and the subject will be advised that she can withdraw at any time.

The subject will be given the opportunity to take the consent home to consider participation. The subject will be asked to read the informed consent form prior to the physician or study coordinator asking the subject any questions concerning their health. Written, informed consent will be obtained after one of the investigators has reviewed the protocol verbally in detail with the subject. The physician will inform the subject that she

has the alternative not to participate in the study. Subjects will receive a signed copy of the consent form for their records. After all questions are answered, and only after the consent form is signed by the patient and one of the MDs listed on the application will study screening commence. Subjects unable to give consent will not be approached.

In cases where the subject is unable to travel to the MGB site for the consent visit, the investigator would call the subject on the phone or over video where details of the study will be discussed. All questions will be answered and the consent form would be sent to the subject electronically along with contact information for the study team. The subject would then review the consent and there would be an additional call to answer if any remaining questions. Once, all questions are answered, the subject would sign and date (including time) the consent form agreeing to their participation in the research and return the signed (handwritten or digital) and dated consent form electronically. The investigator would sign and date (including time) the consent form signed and dated by subject. MGB IRB requirements for digital signatures will be followed when the subjects would prefer to use digital signatures while signing the consent form.

V. Study Procedures

Patients who are eligible would be consented to the study by a physician investigator at Partners. Each subject would then be scheduled and would undergo 2 PET scans over a period of 4 months at the Gordon Center for Medical Imaging at Massachusetts General Hospital as part of the study.

Patients would have up to 3 study visits- the first visit would be for consent (lasting about 1 hour) and 2nd and the 3rd visits would be for the PET/CT (lasting about 3 hours each). The PET/CT appointments may need to be rescheduled depending on the patient's convenience and the availability of time slots.

On the day of the PET scan, if the subject is premenopausal, we would be conducting a STAT quantitative serum hCG test before the scan. Then, a low dose x-ray CT scan will be performed for anatomical localization and for attenuation correction of PET images. An intravenous (IV) catheter would be placed on one arm for the radiotracer (contrast) infusion. An intraarterial catheter would be placed on the arm opposite of the IV line for blood draws that would occur at first every 15 seconds and gradually reduce to 10 minute intervals by the end of the scan. The total volume of blood would be less than 150 ml (10 tablespoons). The PET scan would take about 20 to 60 minutes.

Drug to be use: C-11 Acetate is the tracer used in this study.

Data to be collected: PET and CT images as well as concentration of the radiotracer metabolites in the blood of the patients will be collected

Since [¹¹C]acetate is not a proven early biomarker of rapamycin response, the PET scan data obtained in this study will not be used to adjust the dose of rapamycin that a study participant is given.

Study staff may need to access patient's medical records in Epic to locate the lesion and know the pulmonary function before and/or after the study scan appointment as well as to compare the PET/CT images obtained for the study to other imaging tests obtained for clinical purposes.

VI. Biostatistical Analysis:

We will enroll 8 patients. Assuming a standard deviation of 16% (based on our preclinical in vivo imaging data) for the SUV change between baseline and post-rapamycin/ post-rapalog treatment, a group of 8 patients will allow us to reach 80% power to detect at least a decrease of 7% in [11C]acetate uptake by PET imaging (compared to 11% increase without treatment), using a two-sided one sample t-test at alpha=0.05 level. In fact, we expect to find a greater decrease than 7% in the proposed study, and we will have higher power to detect this greater decrease.

Alternative statistical approach. Assuming a standard deviation of 0.53 (based on prior study (1)) for both a rapamycin/rapalog-naïve and a rapamycin/rapalog-treated group, n= 6 patients per group will allow us to reach 80% power to detect a difference of at least 25% in SUVmax between the two groups using a two-sided two sample t-test at alpha=0.05 level. This statistical approach will allow us to analyze imaging data obtained from two independent groups of patients receiving a single PET scan rather than one group of patients receiving two PET scans each (baseline and after treatment).

VII. Risks and Discomforts

The combined radiation exposure from the PET/CT scan in this study will be not more than 9.4 mSv (4.7 mSv per scan). This amount of radiation is equivalent to 3.75 years of normal background radiation (3.1 mSv exposure = 1 yr background). This level of exposure is considered small and there is no evidence that it represents a major health risk.

Placement of the i.v. catheter may be associated with minor discomfort along with some bruising or swelling at the insertion site. Placement of the intra-arteria catheter could lead to swelling and redness at the sites of line placement, as well as temporary loss of pulse at the wrist. This area may have a bruise or feel uncomfortable for 2-3 days after the catheter is removed.

Inserting an arterial line (A-line) can hurt more than having a regular i.v. or having blood drawn with a needle. The A-line will be placed with local anesthesia (i.e., lidocaine), which may cause an allergic reaction. Even if the wrist area is first numbed, the insertion may still hurt. Once the A-line is in place, it usually does not hurt. Even after the catheter is removed, the site of insertion may feel tender or may have a bruise for 2 to 3 days.

The maximum volume of blood drawn at any scan would be 150cc, which is significantly less than the volume drawn for a blood donation (i.e., ~470cc).

It is possible that incidental abnormal findings may be discovered during a subject's participation in this study. Discovery of incidental findings may prompt study anxiety and follow-up testing.

VIII. Potential Benefits:

Individual subjects enrolled in the study would not benefit directly from the study. In the future, from information obtained in this study, LAM and TSC patients would benefit from a metabolic imaging biomarker in multiple ways. First, a sensitive and specific imaging biomarker would help answer outstanding questions regarding personalized dosage and length of treatment for rapamycin and its analogs (rapalogs). Second, biomarkers of disease progression and therapeutic response would streamline the design, cost and duration of LAM/TSC clinical trials. Third, a metabolic imaging biomarker and circulating VEGF-D could be used as complementary diagnostics to enhance clinical decision making.

IX. Monitoring and Quality Assurance

This study will not be monitored by an independent DSMB.

All unanticipated problems including adverse events will be reported to the Partners Human Research Committee (PHRC) in accordance with the accepted guidelines. A 24-hour/7-day telephone number will be provided for contacting the licensed physician investigator for this purpose.

The research staff will monitor all subjects during their study involvement for evidence of any adverse events.

X. References

1. Verwer...[name], CCR, 2018 Ho CL, Chen S, Ho KM, Chan WK, Leung YL, Cheng KC, Wong KN, Cheung MK, Wong KK. Dual-tracer PET/CT in renal angiomyolipoma and subtypes of renal cell carcinoma. *Clin Nucl Med.* 2012;37(11):1075-82. doi: 10.1097/RLU.0b013e318266cde2. PubMed PMID: 22996247.
2. McCormack FX. Lymphangioleiomyomatosis: a clinical update. *Chest.* 2008;133(2):507-16. Epub 2008/02/07. doi: 133/2/507 [pii] 10.1378/chest.07-0898. PubMed PMID: 18252917.

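### The 80% power for a 7% fall holds only against a fixed, unsourced +11% untreated change; no result against no change from baseline is planned beside it

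*Combined protocol and SAP*

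**What the plan says.** Section VI (Biostatistical Analysis) sizes the paired design at 8 patients, using a two-sided one-sample t-test at the 0.05 level. The variability assumption is a "standard deviation of 16% (based on our preclinical in vivo imaging data"), and the power claim is "80% power to detect at least a decrease of 7% in [11C]acetate uptake by PET imaging (compared to 11% increase without treatment"). The section adds that "we expect to find a greater decrease than 7% in the proposed study", without giving a size. It does not state which value the mean change will be tested against.

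Section II (Specific aims) sets out the scans. For patients not starting therapy: "Patients enrolled who are either on treatment with Rapamycin or a rapalog or not will receive 1 scan each". Those about to start therapy "will receive 2 scans, one at baseline and one after 3 months of therapy". The alternative analysis in Section VI compares "two independent groups of patients receiving a single PET scan". Section II also lists, as one of two expected outcomes, testing acetate PET "as a biomarker of rapamycin activity in TSC2-deficient proliferative lesions".

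**The concern.** A one-sample t-test compares a mean with one fixed number, so its power and its conclusion both depend on that number. Here it appears to be +11%, which is given in a parenthesis and not stated as the null hypothesis. Three things follow.

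- **Source.** The sentence attaches the preclinical attribution to the SD. The 11% may come from the same data, but the text does not say so. It is used as if known without error.
- **No internal check.** Under Section II only patients starting therapy have repeat scans. The alternative analysis compares groups scanned once, so it bears on treatment differences but not on untreated change over time. Neither analysis estimates the quantity that the 11% stands for.
- **Reading of the result.** The plan calls the effect a decrease. A result significant against +11% need not be a demonstrated decrease from baseline, and no analysis against baseline is described that would show the difference.

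At stake is how the paired data are read for the biomarker outcome. If untreated uptake does rise by 11%, the comparison is apt. If it is stable, the same test can credit the drug with an effect that is absent.

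**Working it through.** **Inputs, all from Section VI:** n = 8; SD of change 16%; target change -7%; untreated change +11%; two-sided alpha 0.05; one-sample t-test. Hence df = 7 and critical t = 2.365.

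**Formula.** Noncentrality λ = |δ|·√n / SD, where δ is the true mean change minus the null value. Power = P(|T| > 2.365), with T noncentral t on 7 df.

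**Step 1: reproduce the plan's figure.** Against +11%, δ = -7 - 11 = -18.
- SD 16: λ = 18 × 2.828 / 16 = 3.18; power 77.9%. A simulation with 400,000 replicates gives the same.
- SD 15.57, which rounds to 16: power 80.0%.

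The stated 80% is therefore reproduced within rounding of the inputs.

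**Step 2: could a null of 0 give 80%?** δ = -7; λ = 7 × 2.828 / 16 = 1.24; power 18.9%. Other conventions against 0 give 29.9% (one-sided t), 23.5% (two-sided normal) and 34.2% (one-sided normal). None comes near 80%, which is why +11% is inferred to be the null.

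**Step 3: what 8 patients can show against 0.**

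| True fall from baseline | Power against 0 (n = 8, SD 16%) |
|---|---|
| 7% | 18.9% |
| 18.5% | 80.0% |
| 20% | 85.6% |
| 25% | 96.4% |

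A 7% fall tested against 0 would need 43 patients for 80% power.

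**Step 4: where the two references disagree, if +11% is the analysis null and the observed SD is 16%.**
- Standard error = 16/√8 = 5.66; 95% half-width = 2.365 × 5.66 = 13.4 points.
- Significantly below +11% if the mean is under 11 - 13.4 = -2.4%.
- Significantly below 0 if the mean is under 0 - 13.4 = -13.4%.
- Means between -13.4% and -2.4% are therefore significant against +11% but do not show a fall from baseline.

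The plan's own target, observed exactly, lies in that window. A mean of -7% has a 95% CI of -7 ± 13.4, or -20.4% to +6.4%. Against +11%, t = -18/5.66 = -3.18 and p = 0.015. Against 0, t = -7/5.66 = -1.24 and p = 0.26.

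**Step 5: how often this would happen.** With a true change of -7%, about 77.9 - 18.9 = 59% of trials would be significant against +11% but not against 0 (simulation: 59%). With a true change of -20%, the share is 14% (simulation).

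**Step 6: true change of 0, tested against +11%.** δ = -11; λ = 11 × 2.828 / 16 = 1.94; the test rejects 39.0% of the time.

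**The case against.** The strongest reply is that the plan does what it says. The comparator, target, SD, test, sidedness and alpha all stand in one sentence, and the 18-point contrast can be rebuilt from it. That stands: there is no miscalculation, and the stated 80% need not be changed.

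A reader might infer that the true power is 19% and the trial is badly underpowered. The documents do not support this. The plan never claims 80% power for a fall from baseline. For a marker of drug activity, treated against untreated change is the more relevant contrast, and zero isolates the drug effect only if untreated uptake is stable, which the documents do not show. A reader might also take the 39% as a false-positive rate. It is a false drug-effect claim only if untreated uptake is stable; if untreated uptake rises by 11%, a treated change of 0 is a real effect.

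It is also fair to say that +11% appears in a sample-size justification and that no text fixes it as the null of the final analysis. That stands too, so Steps 4 to 6 are conditional on it. It also shows why the null should be written out.

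Finally, Aim 1 concerns feasibility, success is defined by being able to detect and quantify lesion metabolism, scan data do not alter dosing, and a larger fall is expected. These points limit the severity. They do not dispose of the matter, because the size of the expected fall is not given and the biomarker outcome is one of the two named.

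Section V says that each subject "would undergo 2 PET scans over a period of 4 months", which conflicts with Section II. That is a separate point to reconcile. Even under Section V's wording, Section VI plans no analysis of repeat scans in untreated patients.

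**Conclusion.** The concern holds in a limited form. The power statement is correct for -7% against an assumed +11%. That assumption has no clear source, is treated as exact, and is not checked by any planned analysis. If it serves as the null, an 11-point band of observed means (-13.4% to -2.4%) would be significant without showing a decrease from baseline, and the plan's own target value falls inside it.

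These figures rest on the plan's SD of 16%, which comes from preclinical data, and on the inference that +11% is the null. The first is the plan's assumption; the second is supported by the reproduced power but is not stated. Severity is minor to moderate. The issue shrinks if the fall is as large as the sponsor hopes: power against 0 is 86% at a 20% fall.

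**What to change.** Revise Section VI as follows.

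1. Write out the null hypothesis and give the source of the 11%.
2. Keep the stated 80%, and say that it is for a mean change of -7% against an assumed +11% without treatment.
3. Add that, against no change from baseline and at SD 16%, 8 patients give 80% power for a fall of about 18.5% and about 19% for a 7% fall.
4. Report the mean percent SUV change with its 95% CI (half-width about 13 points at SD 16%) and the test against 0, beside the comparison with +11%.
5. Describe the result as a fall from baseline only if the CI excludes 0. Label any conclusion that rests on +11% as dependent on that external assumption.

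This is a cheap improvement: wording only, with no extra patients or scans. The cost is a less favourable detectable fall on the page. The test against 0 also understates the drug effect if untreated uptake rises, so it should accompany the +11% comparison and not replace it.

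### Does the radiation statement need changing because 9.4 mSv at 3.1 mSv per year is 3.0 years of background, not 3.75?

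*Combined protocol and SAP*

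**What the plan says.** Section VII of the combined protocol and SAP gives the dose first: "The combined radiation exposure from the PET/CT scan in this study will be not more than 9.4 mSv (4.7 mSv per scan". The next sentence converts it, with the conversion rate in brackets: "This amount of radiation is equivalent to 3.75 years of normal background radiation (3.1 mSv exposure = 1 yr background". The section then describes this level of exposure as small.

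Section II (Specific aims) describes two kinds of subject. For one kind, "Patients enrolled who are either on treatment with Rapamycin or a rapalog or not will receive 1 scan each". Those about to start rapamycin or a rapalog "will receive 2 scans, one at baseline and one after 3 months of therapy". Section V (Study Procedures) instead has every subject scanned twice within four months.

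**The concern.** Three numbers in adjacent sentences (a dose, a yearly rate and a number of years) are tied together by one division, and the division fails. At least one of them must be wrong, and the text does not say which. If the years figure is wrong, the comparison only overstates the exposure. If the background rate is wrong, the comparison rests on a mistaken yardstick. If 3.75 was worked out from a different dose, the ceiling of 9.4 mSv would be too low, which would matter in a study that offers its subjects no direct benefit. The ethics committee relies on this section, and an investigator explains the protocol to each subject before consent.

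There is also a question about subjects scanned once. The comparison in years is made only for the combined exposure, so they may seem to have no figure of their own.

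**Working it through.** **Inputs, all from Section VII.** Combined exposure D = 9.4 mSv (a maximum); exposure per scan d = 4.7 mSv; background rate b = 3.1 mSv per year; stated equivalent = 3.75 years.

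**Is the dose consistent with itself?** 2 × d = 2 × 4.7 = 9.4 mSv. Yes.

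**Can the stated years be reproduced?** Years = D / b = 9.4 / 3.1 = 3.03. They cannot: 3.75 / 3.03 = 1.24, so the printed figure is about 24% higher.

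**Could rounding of the inputs explain it?** The lowest quotient is 9.35 / 3.15 = 2.97 and the highest is 9.45 / 3.05 = 3.10. No.

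**Could a different number of scans explain it?**

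| Scans | Dose (mSv) | Years at 3.1 mSv per year |
|---|---|---|
| 1 | 4.7 | 1.52 |
| 2 | 9.4 | 3.03 |
| 3 | 14.1 | 4.55 |

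No whole number of scans gives 3.75.

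**What would give 3.75?**

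- Keeping b = 3.1: the dose would be 3.75 × 3.1 = 11.6 mSv, or 5.8 mSv per scan. That is 11.6 − 9.4 = 2.2 mSv above the stated maximum.
- Keeping D = 9.4: the rate would be 9.4 / 3.75 = 2.51 mSv per year, against the 3.1 printed in the same sentence.

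Neither 11.6 mSv nor 2.5 mSv per year appears anywhere in the document.

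**What uses the years figure?**

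- *Eligibility (Section III):* the radiation criterion concerns exposure in other research studies, set against 50 mSv per year. It does not use background years.
- *Procedures (Section V):* nothing depends on it.
- *Sample size and analysis (Section VI):* these rest on standardized uptake values and their standard deviations. Nothing depends on it.
- *Description of the exposure as small (Section VII):* replacing 3.75 by 3.03 lowers the comparison, so this description is not weakened.

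**Subjects with one scan.** Their dose is printed: "4.7 mSv per scan". The combined dose is worded as a maximum, and 4.7 mSv lies within it. Only the conversion to years is absent, and it is one division: 4.7 / 3.1 = 1.52.

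**The case for a change.** The strongest case for acting is that the source of the error is unknown. Internal consistency does not prove a dose correct: if the per-scan value were wrong, doubling it would carry the error into the total, and 2 × 4.7 = 9.4 would still hold. An exposure of 11.6 mSv therefore cannot be excluded from the text alone, and checking costs one line. A risk statement should also be right for its own sake, since subjects may hear the figure repeated.

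Part of this stands. The three figures do conflict, the documents cannot settle which is wrong, and whoever holds the dosimetry source should reconcile them. What does not stand is the step to a likely understatement of dose. The 11.6 mSv is obtained only by assuming that 3.75 is right and working backwards. The dose appears twice in agreeing form, while 3.75 appears once, as a derived figure. A slip in the conversion is the simpler explanation.

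The point about single-scan subjects does not stand either. Giving the maximum together with the dose per scan is an acceptable way to disclose exposure, and a second figure in years would be an optional extra. The disagreement between Sections II and V on whether everyone has two scans is real, but it is a separate matter and does not produce the 3.75.

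**Conclusion.** The arithmetic is wrong as printed: 3.03 years (2.97 to 3.10 allowing for rounding) against 3.75, an overstatement of about 24% on the stated dose and rate. It is a clerical slip in an explanatory comparison. The quantified risk is the dose in mSv, which is given both per scan and in total. No decision on whom to enroll, how to scan, how many subjects to recruit or how to analyze the data would change, and on the stated inputs the error runs in the cautious direction. Correcting it would tidy the text without improving the design or the conclusions, so no change to the plan is called for.

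This rests on the stated dose and background rate, neither of which can be verified from the documents. If the dosimetry source showed a total above 9.4 mSv, the fault would lie in the dose statement itself and the question would be a different one. Nothing in the text points that way. The consent form is not among the material available, so whether it repeats the 3.75 is unknown.
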